KEY INCLUSION CRITERIA	
Subjects must meet all of the following applicable inclusion criteria to participate in this study:
 
 • Aged \geq 18 years at the time of consent, capable of providing written informed consent and HIPAA authorization for the release of personal health information. • Treatment naïve OR adjuvant greater than 6 months ago (except metastatic colorectal or small bowel cancer; which may have progressed on or be intolerant to fluorouracil/capecitabine, oxaliplatin and irinotecan-based therapy), histologically or cytologically confirmed metastatic/recurrent or locally advanced GI cancers (metastatic/recurrent fact can be radiologically confirmed) • Enrollment no later than 30 days after initiation of the systemic therapy

	
 Ability of the subject to understand and comply with study procedures for the entire length of the study Life expectancy is > 3 months
KEY EXCLUSION CRITERIA	
 Subjects have previously received or are currently receiving LCI Patient Navigation Program services Subjects with colorectal cancer enrolled in the Empower Program Subjects with low grade neuroendocrine tumors
STATISTICAL CONSIDERATIONS	Study is designed with co-primary objectives to evaluate the acute care utilization and 6-month OS rate; the study is primarily powered based on the OS landmark objective. The overall type I error rate for this study is alpha = 0.05, and the co-primary endpoints were both powered at the 2-sided alpha = 0.025 significance level. It is estimated that treatment with standard therapy results in median survival of 8 months, and when assuming an exponential distribution, this corresponds to a 6-month survival rate of approximately 60%. The primary OS objective of this study is designed to test the null hypothesis that the 6-month OS survival rate is $\leq 60\%$. Thus, 300 evaluable subjects, randomized in a one-to-one fashion, will provide 80% power, assuming the true 6-month OS rate with Nurse Navigation is 80% (a 20% improvement in the 6-month OS rate is considered clinically relevant). This sample size will also provide at least 93% power to detect a 20% reduction in acute care visits (assuming there will be 6 acute care utilization visits per year in the control arm).
NUMBER OF SUBJECTS	Up to 347 subjects may need to be enrolled to reach 300 evaluable subjects

SCHEMA

Table 1.

GLOSSARY OF TERMS

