1.3 Study Design

In this study, we plan to recruit 300 patients with gastrointestinal cancers, who are receiving care at LCI. Upon accrual, patients will be randomized 1:1 to receive standard of care plus ONN service (n = 150) or standard of care only (without ONN service; n = 150). Patients in both arms will be assessed for acute care utilization and overall survival (OS) rate at 6 months as primary objectives.

Anticipated accrual period will be 48 months.

We hypothesize that the implementation of a prompt and effective coordination of care provided by ONN will reduce the number of avoidable, unplanned ED visits and hospitalizations, reliance on acute care utilization, and may result in an improvement of patient overall survival.

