11.2 Sample Size

This study is designed with co-primary objectives to evaluate the acute care utilization and 6-month OS rate. Power and sample size calculations were primarily calculated based on the OS landmark objective. The overall type I error rate for this study is alpha = 0.05. Therefore, the co-primary endpoints were both powered at the 2-sided alpha = 0.025 significance level. We estimate that treatment with standard therapy results in median survival of 8 months. Assuming an exponential distribution, this corresponds to a 6-month survival rate of approximately 60%. Therefore, the primary OS objective of this study is designed to test the null hypothesis that the 6-month OS survival rate is \leq 60%. A total of 300 evaluable subjects enrolled in a one-to-one fashion will provide 80% power, assuming the true 6-month OS rate with Nurse Navigation is 80%. A total of 347 subjects may need to be enrolled to achieve 300 evaluable subjects. A 20% improvement in the 6-month OS rate is considered clinically relevant. This sample size will also provide at least 93% power to detect a 20% reduction in acute care visits (assuming there will be 6 acute care utilization visits per year in the control arm).

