11.5 Analysis Methods

11.5.1 Timing of Analysis

An interim analysis will occur after 100 subjects have been enrolled in the evaluable population. A second interim analysis will occur after 85 deaths have occurred in the evaluable population. A third interim analysis will occur after 120 deaths have occurred in the evaluable population. Analyses of the primary objectives will occur after 300 subjects have been enrolled in the evaluable population. A final analysis will occur when the OS censoring rate reduces to 20% or when all surviving subjects (who remain on study) are on study for at least 30 months (whichever occurs first).

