11.5.4 Primary Analysis

The frequency and proportion of subjects alive at 6 months or better will be calculated for each study arm. Corresponding 95% confidence intervals will be estimated using the Clopper-Pearson method. A

two-sided test for binomial proportions will be carried out, testing the null hypothesis that there is no difference in the OS6 rate between the arms.

Poisson regression analyses will be used to analyze acute care utilization visits. Treatment arm will be included in the model as the primary covariate and an asymptotic test of significance will be carried out to compare acute care utilization between the arms.

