11.5.8 Interim Analysis

After 100 subjects have been enrolled in the OS evaluable population, a formal interim analysis will be conducted. The interim analysis is designed primarily to assess futility regarding the 6-month OS rate objective and will be based on the conditional power. If the conditional power falls below 50%, the OS6 objective may be removed from the co-primary objective. If this occurs, the primary objective will be based only on the acute care utilization objective. With this revised design, 158 evaluable subjects would provide 90% power to detect a 20% reduction in acute care utilization from 6 visits per year in the non-navigation arm based on a 2-sided alpha = 0.05 significance level.

If the OS6 conditional power is greater than 50% but less than 80%, the sample size may be increased so that the power for the revised sample size is maintained at 80%. As discussed in Chen et al, 2004, this sample size re-estimation will not inflate the type I error.

Sample size re-estimation

As per protocol, the interim futility analysis occurred on 9/22/2022. Based on the results of the interim analysis and on the initial statistical design, the trial will proceed with OS6 and ACU as co-primary

endpoints. In order to retain 80% power for the OS6 objective, the sample size will be increased from 107 evaluable subjects per arm to 150 evaluable subjects per arm.

In order to achieve a total of 300 evaluable subjects, it is estimated that approximately a total of 347 subjects may be enrolled.

Additionally, ~~an~~ interim efficacy analysisanalyses will be performed after 85 and 120 deaths in the evaluable population have occurred (Interim Efficacy Analysis I and II). This will be conducted under the auspices of the LCI DSMC and will be blinded to the Sponsor-Investigator and the study conduct trial site. If, in the clinical judgement of the LCI DSMC, there are impelling favorable OS trends, the study may be terminated due to ethical considerations. No formal statistical stopping rules will be utilized, and no alpha spend will be incurred due to this interim efficacy evaluation.

As per protocol, Interim Efficacy Analysis I occurred on 1/23/2022. Based on the results of the blinded survival analysis and the updated statistical design (following the interim futility analysis on 9/22/2022), the trial will continue and Interim Efficacy Analysis II will be performed after 120 deaths in the evaluable population have occurred.

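### The stated 80% power for 6-month survival does not follow from 300 evaluable subjects at 60% versus 80%; the planned two-arm test gives about 93–95%

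*Combined protocol and SAP*

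**What the plan says.** Section 11.2 states that "300 evaluable subjects enrolled in a one-to-one fashion will provide 80% power, assuming the true 6-month OS rate with Nurse Navigation is 80" per cent. The synopsis, under Statistical Considerations, has the same claim: "300 evaluable subjects, randomized in a one-to-one fashion, will provide 80% power, assuming the true 6-month OS rate with Nurse Navigation is 80" per cent. The comparator is about 60%, derived from an exponential curve with an 8-month median. On the significance level, 11.2 says "the co-primary endpoints were both powered at the 2-sided alpha = 0.025 significance level". Section 1.3 gives the arm sizes as "standard of care plus ONN service (n = 150) or standard of care only (without ONN service; n = 150", and 11.5.1 ties the primary analysis to the same total: "Analyses of the primary objectives will occur after 300 subjects have been enrolled in the evaluable population".

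The two places that describe the OS6 hypothesis differ. Section 11.2 words the null as a 6-month rate of at most 60%. Section 11.5.4 plans a two-sided two-arm comparison, "testing the null hypothesis that there is no difference in the OS6 rate between the arms", without naming the version of the test.

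Section 11.5.8 gives the history. If conditional power at the interim analysis lies between 50% and 80%, "the sample size may be increased so that the power for the revised sample size is maintained at 80" per cent. It then reports the outcome: "In order to retain 80% power for the OS6 objective, the sample size will be increased from 107 evaluable subjects per arm to 150" per arm.

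**The concern.** A difference of 20 percentage points from a base of 60% is large, and 150 per arm looks generous for 80% power even at alpha 0.025. Section 11.5.8 also shows that the size rose by 40% (from 107 to 150 per arm), while 11.2 and the synopsis give 80% power at the enlarged size, under an effect of 60% versus 80%.

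This is the headline power of the co-primary endpoint on which the trial is mainly sized. As written, a reader cannot tell whether the 80% is fixed-sample power, conditional power given interim data, or power at an effect smaller than the one stated. That matters most for a non-significant OS6 result, where the interpretation depends on which effects the trial could reliably have detected.

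**Working it through.** **Inputs.** Two-sided alpha 0.025, so z = 2.2414 (11.2). Control rate 0.60 and navigation rate 0.80 (11.2). n = 150 per arm (1.3), previously 107 per arm (11.5.8). Two-arm test of proportions (11.5.4). The control rate follows from the plan's own median: exp(−ln 2 × 6/8) = 0.595, rounded there to 60%.

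**Formula, pooled z.** Power = Φ[(d − z·SE₀)/SE₁], with d = 0.20, SE₀ = √(2 × 0.7 × 0.3/n) and SE₁ = √((0.24 + 0.16)/n). The continuity-corrected version replaces d by d − 1/n in the numerator. The unpooled version is Φ(d/SE₁ − z).

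**Where 80% does reproduce: n = 107.** SE₀ = 0.06265 and SE₁ = 0.06114.
- Pooled: (0.2 − 0.1404)/0.06114 = 0.974, power 83.5%.
- Continuity-corrected: (0.2 − 0.0093 − 0.1404)/0.06114 = 0.821, power 79.4%.
- Fisher's exact test, by enumeration: 80.2%.

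**At the stated size: n = 150.** SE₀ = 0.05292 and SE₁ = 0.05164.
- Pooled: (0.2 − 0.1186)/0.05164 = 1.576, power 94.3%.
- Continuity-corrected: (0.2 − 0.0067 − 0.1186)/0.05164 = 1.447, power 92.6%.
- Unpooled: 3.873 − 2.241 = 1.632, power 94.9%.
- Fisher, by enumeration: 92.9%.

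| Test | Power at 107/arm | Power at 150/arm | n/arm for 80% |
|---|---|---|---|
| Fisher exact | 80.2% | 92.9% | 107 |
| z, continuity-corrected | 79.4% | 92.6% | 109 |
| z, pooled | 83.5% | 94.3% | 99 |
| z, unpooled | 84.8% | 94.9% | 96 |

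**Sensitivity.** Using the unrounded control rate of 59.5% raises power at 150 per arm to 94.1% (Fisher), 93.9% (continuity-corrected) and 95.3% (pooled). Taking the null literally as 11.2 words it (150 navigated subjects against a fixed 60%, upper tail 0.0125, reject at 104 or more alive) gives 99.9%. No variant falls to 80%. In reverse, 80% power at 150 per arm corresponds to 60% versus 76.3–77.1%, an effect the plan does not adopt.

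**Conditional-power reading.** Assume 50 per arm at the interim analysis (11.5.8 gives 100 in total) and a normal approximation. With interim statistic z₁, t = 50/N and drift θ per √n, conditional power = Φ[(z₁√t + θ√N(1 − t) − 2.2414)/√(1 − t)].
- *Interim trend continues* (θ = z₁/√50). Conditional power of 80% at N = 150 requires z₁ = 1.691. At N = 107 the same z₁ gives (2.473 − 2.241)/0.730 = 0.318, or 62%. This lies inside the 50–80% zone.
- *Stated 60% versus 80% effect for the remainder* (θ = 0.2/√0.4 = 0.316). Conditional power of 80% at N = 150 requires z₁ = 0.600. At N = 107 this gives (2.153 − 2.241)/0.730 = −0.121, or 45% (45–47% depending on the variance used). This is below the 50% floor. Conversely, 50% to 80% at 107 per arm corresponds to 82% to 94% at 150.

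**Supporting sign of carried-over text.** The acute care claim in 11.2 of at least 93% power also matches the earlier size. Under a Poisson model with 6 versus 4.8 visits per year, one year of follow-up per subject (an assumption) and alpha 0.025, 107 per arm gives 93.7% and 150 per arm gives 98.7%. That claim is still true at 150, so it is only circumstantial.

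**The case against.** The strongest reply is that 11.5.8 already explains the pairing of 80% with 150 per arm: a conditional-power rule operated, and the size was raised to restore 80%. Under the interim trend, the arithmetic fits that rule. On this view, the only lapse is a missing label and cross-reference in 11.2 and the synopsis. Part of this stands. Section 11.5.8 does account for the number 150, and the trend-based reading is plausible. But 11.5.8 never says whether its 80% is conditional or which effect was assumed for the remainder. Section 11.2 and the synopsis mention no conditioning and explicitly assume a true rate of 80%. The reading that fits the rule contradicts that assumption, and the reading that keeps it misses the rule's floor. Whether the 80% is conditional power or text left from the 107-per-arm design cannot be settled from the documents.

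A second reply is that 93% could mislead, because the trial was not a fixed 300-subject design. This is fair as a caution. A simulation of the whole design under 60% versus 80% (50 per arm at the interim, pooled z) gave 72–86% if OS6 is always dropped when conditional power is below 50%, and 86–89% if it is never dropped. These figures depend on an optional rule and average over trials that stop at 107 per arm, so they are not the power of 300 subjects. Among simulated trials that entered the increase zone, power at 150 per arm was 90–95%. The caution is met by calling 93% fixed-sample power.

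Third, the consequence is small because the misstatement is conservative at the stated effect. That is correct, and it limits the weight of the point.

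**Conclusion.** The sentence is wrong as written in both places. At 150 evaluable subjects per arm, 60% versus 80% and two-sided alpha 0.025, fixed-sample power is 92.6–94.9%, not 80%: an understatement of about 13 to 15 percentage points. For 80% power at that effect, 96 to 109 per arm suffice.

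The result rests on equal arms, independent subjects and an unstratified two-sample test. The choice among standard versions of the test moves it by little more than 2 points. The conditional-power comparison also assumes 50 per arm at the interim analysis. None of this shows that 300 is the wrong size, that the trial is underpowered, or that alpha or the analysis needs to change. The mismatch in the null hypothesis between 11.2 and 11.5.4 is a separate wording fault in the same paragraph and does not explain the discrepancy.

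**What to change.** In 11.2 and in the synopsis, state that 150 evaluable subjects per arm give about 93% fixed-sample power for 6-month survival of 60% versus 80% at two-sided alpha 0.025, and name the test (92.9% is Fisher; uncorrected z-tests give 94–95%). Refer to 11.5.8 for the increase from 107 to 150 per arm.

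If the 80% is to stay, say what it is: either conditional power at the interim analysis, with the effect assumed for the rest of the trial, or power at a revised effect, with its value.

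In the same edit, word the OS6 null in 11.2 and the synopsis as no difference between arms, to match 11.5.4.

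The cost is wording in two places. Patients, conduct and analysis are unchanged.

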11.3 Endpoints

11.3.1 Definition of Primary Endpoints

Overall survival at 6 months (OS6) will be determined as a binary variable indicating whether or not the subject was alive at 6 months following randomization.

Acute care utilization visits will be calculated for each subject as the total number of acute care visits normalized to an annual basis. Acute care visits will include unplanned hospital admissions, ED visits, and urgent care visits.

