2. STUDY OBJECTIVES

2.1 Objectives

2.1.1 Primary Objective

- The co-primary objectives of this study are to examine the impact of Oncology Nurse Navigation program on patient **Acute Care Utilization**, defined as unplanned inpatient admissions, emergency room encounters, and/or urgent care visits, and **overall survival rate at 6 months**.

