6. STUDY CALENDAR

Table 2. Study Procedures and assessments

Study Procedures	Registration	Baseline ²	During the Intervention ⁸	Off-intervention ⁹	Survival Follow-up
Informed Consent	X				
Demographics¹		X			
Medical History³		X			
Adherence to clinical care⁴			Continuously throughout the study from Randomization to Off-intervention every 3 months¹¹		
Acute Care Utilization⁵					
Collection of subject's hospital admission and discharge dates⁶					
Survival assessment			X¹⁰		
Subject satisfaction survey			X ⁷	X ⁷	

Key to Footnotes

¹ Demographic information will include: DOB, sex, race, live-in caregiver status, income, insurance status, education level, zip code.

² Screening window is at most 28 days prior to enrollment.

³ The following baseline medical history information will be manually collected from EMR: smoker status, diabetes, ETOH use, BMI, weight, clinically significant pre-existing conditions, and treatment and procedure history.

⁴ Collect the number of visits scheduled for the subject and the number of no-shows, to include all visits scheduled within Atrium Health, not just oncology related.

⁵ Collect unplanned inpatient hospital admissions, emergency room encounters, and urgent care visits.

⁶ Hospitalization encounter is temporally defined as a difference between date of discharge and subtracted date of admission.

⁷ Assessed by a EORTC IL109 customized questionnaire ([Appendix B](#)). It will be collected in two time points. 1st survey will be collected at 4 weeks +2 weeks after the randomization, 2nd survey at 10-14 weeks from the randomization. Subjects will be offered the option to provide survey responses electronically or during a clinic visit. If subject is not able to complete a survey during the study window, they will be asked to complete at the next scheduled in-person visit. This will NOT be considered as a protocol deviation.

⁸ If subject remains on study after the relocation from one LCI site to another LCI site, subject will remain on their original arm he/she was randomized to.

⁹ Subject will become off-intervention and enter the survival follow-up after meeting the criteria for off-intervention, [Section 8.1](#).

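### The acute care count has no rule for an ED visit that ends in admission; if both records count, the plain Poisson test is too liberal and a change of admission route can look like fewer visits

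*Combined protocol and SAP*

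**What the plan says.** The endpoint is a per-patient total: "Acute care utilization visits will be calculated for each subject as the total number of acute care visits normalized to an annual basis" (Section 11.3.1). The next sentence lists the components: "Acute care visits will include unplanned hospital admissions, ED visits, and urgent care visits". The primary objective (Section 2.1.1) gives the same three types, "defined as unplanned inpatient admissions, emergency room encounters, and/or urgent care visits". Data collection follows the same list: "Collect unplanned inpatient hospital admissions, emergency room encounters, and urgent care visits" (Study Calendar, footnote 5; Section 7.2 agrees).

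No section says whether an ED visit and the admission it leads to are one visit or two, or whether linked records are merged. By contrast, length of stay, a secondary endpoint, is defined in Section 11.3.2 down to the added day.

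For the analysis, "Poisson regression analyses will be used to analyze acute care utilization visits", with arm as the primary covariate, and "an asymptotic test of significance will be carried out to compare acute care utilization between the arms" (Section 11.5.4). No overdispersion term, robust variance or negative binomial alternative is named. Section 11.2 says that "the co-primary endpoints were both powered at the 2-sided alpha = 0.025 significance level" and sizes the endpoint for a 20% reduction, "assuming there will be 6 acute care utilization visits per year in the control arm". It does not say whether those 6 are encounters or episodes.

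**The concern.** Many unplanned admissions begin in an emergency department. If the three encounter types are simply added, an episode that passes through the ED contributes 2 and a direct unplanned admission contributes 1. Two consequences follow.

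- **Variance.** Paired records arrive together, so the count varies more than a Poisson variable with the same mean. A test that fixes the variance at the mean then rejects too often under the null.
- **Meaning of the effect.** The weight of an admission depends on its route. Navigators coordinate appointments, expedite referrals and care, and act as the patient's central contact (Sections 1.1.8 and 5.1). If that changes how patients reach the hospital, the count can fall with no fall in acute episodes. A better standard error would not cure this.

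The silence matters even without these effects, because two analysts could derive different co-primary results from the same records.

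**Working it through.** **Inputs from the documents.** Control rate 6 per year, 20% reduction (to 4.8), two-sided alpha 0.025, 300 evaluable patients randomised 1:1, so 150 per arm (Section 11.2). An acute-care-only design with 158 patients, 90% power and alpha 0.05, and the increase from 107 to 150 per arm (Section 11.5.8).

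**Assumptions.** f, the share of acute episodes that produce both an ED (or urgent care) record and an admission record, is not in the documents; 0.2 to 0.6 is shown. One year of exposure per patient is also assumed. The plan's own figures imply it, but Section 5.4 collects acute care data only until the patient comes off intervention.

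**1. The plan's own figures.** With variance equal to the mean:

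n per arm = (1.960 + 1.282)² × (6 + 4.8) / (6 − 4.8)² = 78.8, so 79 per arm and 158 in total, an exact match.

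Power at alpha 0.025 is Φ(1.2 / √(10.8/n) − 2.2414):
- n = 107: Φ(3.777 − 2.241) = 93.8%
- n = 150: Φ(4.472 − 2.241) = 98.7%

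The stated 93% or more matches 107 per arm and remains true as a lower bound at 150. The sizing therefore rests on pure Poisson variance.

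**2. Variance if both records count.** Let episodes be Poisson, each contributing m = 2 with probability f and m = 1 otherwise. Then E[m] = 1 + f, E[m²] = 1 + 3f, and

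variance/mean = φ = (1 + 3f)/(1 + f).

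The Poisson standard error is too small by 1 − 1/√φ, and the two-sided error at nominal 0.025 is 2[1 − Φ(2.2414/√φ)].

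| f | φ | SE too small by | Error at nominal 0.025 |
|---|---|---|---|
| 0.2 | 1.6/1.2 = 1.33 | 13% | 0.052 |
| 0.4 | 2.2/1.4 = 1.57 | 20% | 0.074 |
| 0.6 | 2.8/1.6 = 1.75 | 24% | 0.090 |

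A simulation of 100,000 trials (150 per arm, one year) gave 0.063 at f = 0.3 (formula 0.064) and 0.082 at f = 0.5 (formula 0.083). Counting each episode once gave 0.025 in both cases. Neither the formula nor the simulation includes variation between patients.

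**3. Route effect.** With the same episode rate in both arms, the count ratio is (1 + f in the navigation arm)/(1 + f in the control arm):
- 0.4 to 0.3: 1.3/1.4 = 0.93
- 0.4 to 0.2: 1.2/1.4 = 0.86
- 0.5 to 0.2: 1.2/1.5 = 0.80, the size of the design effect

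**4. Power if each episode counts once.** If the 6 per year already means episodes, power at 150 per arm stays at 98.7%. If it includes duplicates, the episode rate is λ = 6/(1 + f), and power is Φ(0.2λ / √(1.8λ/150) − 2.2414):

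| f | λ | Power, one year |
|---|---|---|
| 0.2 | 5.00 | 96.7% |
| 0.4 | 4.29 | 93.8% |
| 0.5 | 4.00 | 92.1% |
| 0.6 | 3.75 | 90.2% |

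With an assumed mean exposure of half a year, power is about 82% with no duplicates, 74% at f = 0.2 and 60% at f = 0.6.

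**The case against.** The strongest reply has four parts.

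- **The text does not say two.** A reader might infer that the plan defines an ED visit ending in admission as two visits. It does not. It lists what is included and is silent on linked records, and the and/or in the objective leaves a count-once reading open. This stands, so both consequences are conditional on the count-both reading.
- **The variance problem is broader than double counting.** A patient-level robust variance or a dispersion term would correct the standard error even if both records count, and counting once would leave variation between patients. This also stands. It is why the fix needs both a counting rule and a variance method.
- **A route change need not be spurious.** The Synopsis and Section 1.3 hypothesise fewer unplanned ED visits as well as fewer hospitalisations, and Section 1.1.4 speaks of keeping patients out of the ED. An avoided ED visit can be a real benefit, and encounters and episodes are both defensible units. No section says that navigators arrange direct admissions, and whether an arranged admission is still unplanned is undefined. What remains is that the sum alone cannot show which kind of change occurred.
- **Interim analyses have already taken place** (Section 11.5.8), so changing the unit of a co-primary endpoint now could look data-driven. This is a fair caution about how the decision is taken. It does not justify leaving the unit undefined.

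**Conclusion.** The concern holds in conditional form. The co-primary count lacks a rule for linked records, and its most literal derivation counts an ED visit ending in admission twice. On that derivation, the model-based Poisson test has a two-sided error of about 5% to 9% against the allotted 2.5% for an assumed f of 0.2 to 0.6, before variation between patients is considered.

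A reader might take 5% to 9% as this trial's actual error rate. The documents do not support that: they give no f, do not fix the counting rule, and do not state the variance estimator. Likewise, the ratio of 0.93 is a scenario. It needs f to differ between arms, and nothing in the documents shows that it would.

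This is more than a request for missing detail. A count-once rule makes the endpoint reproducible and brings it closer to the variance assumption on which the figure of 158 depends. It should be settled before the primary analysis.

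**What to change.** Decide the following blind to arm-level results and document it before the primary analysis:

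1. Count an ED or urgent care visit that leads to an unplanned admission on the same or next calendar day once, as an admission. The window is a proposal; what matters is that it is fixed in advance.
2. State whether the 6 visits per year in Section 11.2 means encounters or episodes.
3. Report unplanned admissions, ED visits and urgent care visits separately by arm, so that a change of route is visible.
4. Keep the raw sum of all records as a sensitivity analysis.
5. In Section 11.5.4, name a robust or dispersion-adjusted variance for the Poisson model, because counting once removes only this source of overdispersion.

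**Cost.** One derivation rule and one sentence on variance. The sponsor should confirm that ED and urgent care dates are recorded, because the Study Calendar and Section 7.2 name only admission and discharge dates. If the 6 per year included duplicates, some power is lost: at 150 per arm with one year of exposure, 98.7% falls to 96.7% at f = 0.2 and 90.2% at f = 0.6. In that case the power statement in Section 11.2 should be restated in episodes; it drops below 93% somewhere between f = 0.4 and f = 0.5.
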